Section 1.3.3 Schedule of Activities Part 2 Panel B	Addition of a safety laboratory assessment time-point for Panel B in each period of Part 2.	CCI [REDACTED]

Section Number and Name	Description of Change	Brief Rationale
Additional Changes		
Section 1.1 Synopsis	Addition of Panel B (approximately 12 participants) at MK-6552 dose levels of 1 mg to 4 mg.	CCI [REDACTED]
Section 1.1 Synopsis	Changes to the primary safety objective.	To add the safety assessment of multiple day dosing when MK-6552 CCI [REDACTED]
Section 1.1 Synopsis	Changes to the primary PD objective.	CCI [REDACTED]
Section 1.1 Synopsis	Updated the estimated duration of study from 11 to 17 months	To account for the additional 12 participants in Panel B.
Section 1.1 Synopsis	Updated the approximate number of participants in the study from 12 to 24.	To account for the additional Panel B.
Section 1.1 Synopsis	Updated the Intervention Groups and Duration table.	To add the new dosage levels and corresponding treatment periods of Panel B.
Section 1.1 Synopsis	Updated the Total Number of Intervention Groups/Arms from 4 to 7.	To add the new dosage levels of Panel B.
Section 1.1 Synopsis	Updated overall Duration of Participation from 11 to 14 weeks.	To account for the updated screening period of 5 weeks and number of intervention weeks from 5 to 7 due to natural scheduling of treatment period every ~7 days by the sites.
Section 1.2 Schema	Addition of Panel B with corresponding 4 sequential treatment periods of 1 mg to 4 mg.	To account for the additional Panel B at the higher dose levels.
Section 1.2 Schema	Study Diagram figure was updated to reflect the dose levels in Panels A and B	To account for the additional Panel B at the higher dose levels.
Section 1.3.1 Schedule of Activities Part 1	Removed the specific number of days for the EDS SOC Washout Period	To provide more flexibility in the washout duration requirements due to different prior medications taken by the participants.
Section 1.3.1 Schedule of Activities Part 1	Added the screening period window of +/- 7 days.	To clarify previous language stating “approximately 28 days”.
Section 1.3.1 Schedule of Activities Part 1	Added “All Panels” to the first row of the SoA Part 1 table	To clarify that the Part 1 SoA is applicable to Panel A and Panel B.
Section 1.3.1 Schedule of Activities Part 1	Added fasting requirements on the “Standard Meals” row of the table.	To clarify the requirement for fasting in the SoA Part 1 Table.
Section 1.3.1 Schedule of Activities Part 1	Removed note that allowed the predose safety lab assessment to be collected the evening before planned dosing.	To address a discrepancy with the fasting requirement. Since fasting is required before safety lab blood collection, operationally, the procedure cannot be completed the evening before dosing.
Section 1.3.2 Schedule of Activities Part 2 Panel A	Added “Panel A” to the first row of the SoA Part 2 Panel A table	To clarify that this SoA table is applicable only to Panel A.
Section 1.3.2 Schedule of Activities Part 2 Panel A	Removed 16h time-point from the SoA Part 2 Panel A table.	To address a typo. There are no procedures performed at the 16h time-point in the study.

Section Number and Name	Description of Change	Brief Rationale
Section 1.3.2 Schedule of Activities Part 2 Panel A	Added fasting requirements on the “Standard Meals” row of the table.	To clarify the requirement for fasting in Part 2 Panel A.
Section 1.3.2 Schedule of Activities Part 2 Panel A	Removed note that allowed the predose safety lab assessment to be collected the evening before planned dosing.	To address a discrepancy with the fasting requirement. Since fasting is required before safety lab blood collection, operationally, the procedure cannot be completed the evening before dosing.
Section 1.3.2 Schedule of Activities Part 2 Panel A	Removed the “predose” mention in the note column for the standard meals row.	To clarify that fasting is needed before all safety time-points including predose and 24 hours postdose unless mentioned otherwise.
Section 1.3.3 Schedule of Activities Part 2 Panel B	Added SoA Part 2 Panel B table	To account for the added Panel B in the study where some of the procedures have been modified.
Section 1.3.3 Schedule of Activities Part 2 Panel B	Added detail in Notes field for “Standard Meals” row around fasting requirement on Day 4 of each period.	To clarify that although there is a safety lab blood collection on Day 4 of each period, participants do not need to fast on that day.
Section 1.3.3 Schedule of Activities Part 2 Panel B	Added Day 4 safety lab assessment blood collection.	CCI [REDACTED]
Section 2.1 Study Rational	Rationale to assess higher dose range of MK-6552 was added	To account for the additional Panel B at the higher dose levels.
Section 2.2.2 Preclinical and Clinical Studies	Updated PN001 and PN005 completed study summaries.	To further clarify the design of PN001 and provide the updated study status of PN005.
Section 2.2.2 Preclinical and Clinical Studies	Added PK data from PN005.	To add the final PK data from PN005 that is now completed.
Section 2.2.3 Ongoing Clinical studies	Added clinical summary from ongoing PN002, 003 and 007.	To provide an update on the ongoing clinical conduct and available preliminary safety data.
Section 2.2.3 Ongoing Clinical studies	CCI [REDACTED]	CCI [REDACTED]
Section 3 Hypotheses, Objectives and Endpoints	Changes to the primary safety objective.	To add the safety assessment of multiple day dosing when MK-6552 is administered bid 6 hours apart.
Section 3 Hypotheses, Objectives and Endpoints	Changes to the primary PD objective.	To add the PD assessment of multiple day dosing when MK-6552 is administered [REDACTED] CCI
Section 3 Hypotheses, Objectives and Endpoints	Changes to the exploratory PD objective	To add the PD assessment of a single day dosing when MK-6552 is administered [REDACTED] CCI
Section 4.1 Overall Design	Updated the study design with the additional Panel B participants and corresponding doses.	To account for the assessment of higher doses of MK-6552 on safety, PK and PD in an additional 12 participants.
Section 4.1 Overall Design	CCI [REDACTED]	CCI [REDACTED]
Section 4.1 Overall Design	Added the additional visit to the site on Day 4 site for Panel B participants for safety lab assessment blood collection.	CCI [REDACTED]

Section Number and Name	Description of Change	Brief Rationale
Section 4.2 Scientific Rational for Study Design	Added the rationale for study design of Panel B.	To account for the additional Panel B at the higher dose levels.
Section 4.2 Scientific Rational for Study Design	Updated clinical half-life of MK-6552	To provide an updated half-life based on the totality of the data acquired in HV.
Section 4.2.1.1 Safety Endpoints	Doses and dosing duration were updated from ongoing clinical studies and current study.	To provide the updated doses and dosing durations that are investigated in HV or will be investigated in NT1 participants
Section 4.2.1.1 Safety Endpoints	CCI [REDACTED]	To monitor participant safety labs as participants receive multiple higher doses of MK-6552.
Section 4.3 Justification for Dose	Justification to assess higher dose range in Panel B was added.	To account for the additional Panel B at the higher dose levels.
Section 4.3 Justification for Dose	CCI [REDACTED]	CCI [REDACTED]
Section 4.3 Justification for Dose	Table 2 was added to summarize CCI [REDACTED]	To provide supporting data justifying the assessment of higher dose range in Panel B.
Section 4.3.1 Starting Dose for This Study	CCI [REDACTED]	CCI [REDACTED]
Section 4.3.2 Maximum Dose Exposure for This Study	Projected CCI [REDACTED]	To account for the additional Panel B at the higher dose levels.
Section 4.3.2 Maximum Dose Exposure for This Study	Added summary of PK and safety from ongoing PN002.	CCI [REDACTED]
Section 4.3.2 Maximum Dose Exposure for This Study	CCI [REDACTED]	To provide an update on latest safety data obtained in PN002 study.
Section 4.3.3 Rationale for Dose Interval and Study Design	Updated with the Panel B dose levels and study design.	To account for the additional Panel B at the higher dose levels.
Section 5.2 Exclusion Criteria	Removed CrCl wording from EC#5.	To correct a typo. Only eGFR criteria is to be used to assess kidney function.
Section 5.3.1.1 Diet Restrictions	Added fasting requirements before safety lab assessment blood collection.	To clarify on which days participants must fast due to safety lab assessments.
Section 5.3.3 Activity Restrictions	Added the activity restriction requirements for participants that don't need to washout from EDS SOC.	To clarify that participants that don't required a washout from EDS SOC must also avoid activities requiring high degree of attention such as driving a car.
Section 6.1 Study Intervention(s) Administered	Updated the Study Intervention Table with Panel B dosage levels and corresponding Treatment Periods.	To account for the addition of Panel B to the study.
Section 6.3.1 Intervention Assignment	Updated Allocation of Participants to Treatment Table with Panel B information.	To account for the addition of Panel B 4 sequential Treatment Periods in Part 1 and 2-period cross-over in Part 2.

Section Number and Name	Description of Change	Brief Rationale
Section 7.1.1 Individual Stopping Criteria	CCI [REDACTED]	CCI [REDACTED]
Section 8.1.5.1 Prior Medications	Added study restrictions period for participants that don't required a EDS SOC washout.	To clarify the study restriction period for participants that don't require a Washout Period before randomization.
Section 8.1.8.1 Timing of Dose Administration	Added information around timing of dose administration for participants in Panel B.	To account CCI [REDACTED]
Section 8.3.10.1 Safety Phone Calls During the Screening Period	Modified the language around a specific number of days for the safety phone calls.	To add flexibility for participants on concomitant medications that require a different number of safety phone calls based on washout requirement that may differ from EDS SOC listed.
Section 8.3.10.2 Compliance and Safety Phone Calls in Part 2 Days 2 to 6	Added frequency of dosing for participants in Panel B.	To account for the participants in Panel B that must take their study medication at home 6 hours apart.
Section 8.4.4 Regulatory Reporting Requirements for SAE	Added a note to specify that the Sponsor will report SUSARs to the Eudravigilance database via E2B(R3) electronic ICSR form in compliance with CTR 536/2014.	For completeness, for applicable studies, the process to report SUSARs to the Eudravigilance database has been added.
Section 8.11.1 Screening	Added the screening period window of 1 week (+/- 7 days).	To clarify previous language stating, "approximately 4 weeks".
Section 8.11.5 Critical Procedures Based on Study Objectives: Timing of Procedure	Remove safety lab tests from the procedures list that can be completed within 24 hours of dosing.	To address a discrepancy with the fasting requirement. Since fasting is required before safety lab blood collection, operationally, the procedure can't be completed the evening before planning dosing.
Section 8.11.5 Critical Procedures Based on Study Objectives: Timing of Procedure	Added safety lab tests procedure window.	To provide flexibility around the Part 2 Day 4 visit needed for the participant in Panel B.
Section 9.5.2	Added the new panel to the pharmacodynamic models.	To be more explicit that separate models are run for each panel and each of the two timepoints.
Section 9.5.3	Minor adjustment for dose proportionality subsection for language about new panel.	To be more explicit that analysis may be done for each panel separately since completely different subjects at two different dose ranges between the two panels
Section 10.1.1 Code of Conduct for Interventional Clinical Trials	Added Regulation (EU) 536/2014 to the list of regulations that MSD clinical trials is in compliance with.	To clarify that the Sponsor is in compliance with EU CTR 536/2014.

1 PROTOCOL SUMMARY

1.1 Synopsis

Protocol Title: A Two-Part Study to Assess the Safety, Tolerability, Pharmacokinetics and Sleep Latency Effects of MK-6552 in Participants with Narcolepsy Type 1

Short Title: A Safety, Pharmacokinetic and Pharmacodynamic Study of MK-6552 in Participants with Narcolepsy Type 1

Acronym: N/A

Hypotheses, Objectives, and Endpoints:

Hypotheses are aligned with objectives in the Objectives and Endpoints table.

Participants with NT1 18 to 55 years of age inclusive.

Primary Objective	Primary Endpoint
To evaluate the safety and tolerability of a single-day CCI [REDACTED] and multiple-day CCI [REDACTED] administration of MK-6552 in participants with Narcolepsy Type 1.	Adverse events, discontinuation of study intervention due to adverse events
To assess the pharmacodynamic profile of MK-6552 bid CCI [REDACTED] after multiple-day administration in participants with Narcolepsy Type 1. CCI [REDACTED]	Maintenance of wakefulness test trial conducted one hour after each dose on CCI [REDACTED]
Secondary Objectives	Secondary Endpoints
CCI [REDACTED]	CCI [REDACTED]
CCI [REDACTED]	

Overall Design:

Study Phase	Phase 1
Primary Purpose	Treatment
Indication	Narcolepsy
Population	Participants with narcolepsy type 1
Study Type	Interventional
Intervention Model	Sequential This is a multi site study.
Type of Control	Placebo
Study Blinding	Unblinded open-label study Part 1 Double-blind study Part 2
Blinding Roles	No blinding for study Part 1 Participants or Subjects for study Part 2
	Investigator for study Part 2
	Sponsor for study Part 2
Estimated Duration of Study	The Sponsor estimates that the study will require approximately 17 months from the time the first participant (or their legally acceptable representative) provides documented informed consent until the last participant's last study-related contact.

Number of Participants:

Approximately 24 participants will be randomized in the study in order to provide evaluable data on 16 participants (minimum of n=8 per panel).

Intervention Groups and Duration:

[illegible]

Total Number of Intervention Groups/Arms	7
Duration of Participation	Each participant will participate in the study for approximately 14 weeks, from the time the participant provides documented informed consent through the final contact. After a screening phase of up to 5 weeks, each participant will receive assigned intervention for approximately 7 weeks. After the end of treatment each participant will be followed for 2 weeks.

Study Governance Committees:

Executive Oversight Committee	No
External Data Monitoring Committee	No
Clinical Adjudication Committee	No

There are no governance committees in this study. Regulatory, ethical and study oversight considerations are outlined in Appendix 1.

Study Accepts Healthy Participants: No

A list of abbreviations is in Appendix 12.

1.2 Schema

The study design is depicted in [Table 1](#) and [Figure 1](#).

Table 1 Study Schema

Part 1- Panel A ^{a,b,c}			
Period 1 ^d	Period 2 ^d	Period 3 ^d	Period 4 ^d
CCI	CCI	CCI mg	CCI
Part 1- Panel B ^{a,b,c}			
Period 1 ^d	Period 2 ^d	Period 3 ^d	Period 4 ^d
CCI	CCI	CCI mg	CCI
Part 2- Panel A ^{e,f,g}			
Period 1 ⁱ		Period 2	
CCI MK-6552/PBO		CCI MK-6552/PBO	
Part 2- Panel B ^{f,g,h}			
Period 1 ⁱ		Period 2	
CCI MK-6552/PBO		CCI MK-6552/PBO	

^a The suggested doses (with the exception of the starting dose) may be adjusted downward based on evaluation of safety, tolerability, and pharmacokinetic data observed in previous intervention periods. Refer to Section 6.6 (Dose Modification) and Section 7.1.1 (Individual Stopping Criteria) for the safety data that will be reviewed prior to dose escalation.
 
^b Part 1 of the study will be open label in which all participants will receive MK-6552.
 
^c In Part 1, MK-6552 will be administered CCI in each treatment period.
 
^d At least 4 days will separate study drug administration in between periods of Part 1.
 
^e In Part 2 Panel A, MK-6552/PBO will be administered CCI in each treatment period.
 
^f The suggested dose may be adjusted downward based on evaluation of safety, tolerability, and available pharmacokinetic data from Part 1.
 
^g At least 4 days will separate study drug administration in between Part 1 and Part 2 of the study.
 
^h In Part 2 Panel B, MK-6552/PBO will be administered CCI
 
ⁱ At least 2 days will separate study drug administration between periods of Part 2.
 
PBO=placebo, bid=twice a day.
			

Figure 1 Study Diagram

1.3 Schedule of Activities

1.3.1 Part 1

Part 1/All Panels/All Periods/Dose 1 and Dose 2 ^a																
Study Period:	Screening		Intervention													Notes:
Scheduled Day	Screening/Rescreening ^b	EDS SOC Washout Before Randomization (Remote Visit Through Phone Call)	D1												D2	Screening procedures to be completed within approximately 28 days ± 7 days from randomization
CCI			CCI													
Administrative/Study Procedures																
Informed Consent	X															Sec. 5.1, 8.1.1.1
Informed Consent for FBR	X															Sec. 5.1, 8.1.1.2
Participant ID Card	X		X													Sec. 8.1.3
Inclusion/Exclusion Criteria	X		X													Sec 5, 1, 5.2, 8.1.2 Review of inclusion/exclusion criteria will occur at Screening and after predose procedures (if applicable) in Period 1 only. Based on IC/EC, only specific criteria will be reviewed at predose (Period 1 only) prior to randomization.
Medical History	X	X	X													Sec. 8.1.4 Substances: Includes substance usage (drugs, alcohol, tobacco, and caffeine).
Prior/Concomitant Medication Review	X	X	X	X	X	X	X	X	X	X	X	X	X	X	X	Sec. 5.2, 6.5, 8.1.5

Part 1/All Panels/All Periods/Dose 1 and Dose 2 ^a																
Study Period:	Screening		Intervention													Notes:
Scheduled Day	Screening/Rescreening ^b	EDS SOC Washout Before Randomization (Remote Visit Through Phone Call)	D1											D2	Screening procedures to be completed within approximately 28 days ± 7 days from randomization	
CCI			CCI													
Assignment of Screening Number	X															Sec. 8.1.6 Any participant who is screened multiple times will retain the original screening number assigned at the initial Screening Visit.
Assignment of Randomization Number			X													Sec. 5.5, 8.1.7
MK-6552 Administration				X							X					Sec. 8.1.8.1 In each treatment period, a second dose of study intervention ~ 6 hours (+/- 30 mins) following the first dose will be administered to participants
Domiciling			X	X	X	X	X	X	X	X	X	X	X	X	X	Sec. 8.1.11 In each treatment period, participants will report to the CRU the day before (Day -1) the first scheduled day of study intervention administration and remain in the unit at least up to 24-hours postdose #2

25

Part 1/All Panels/All Periods/Dose 1 and Dose 2 ^a																	
Study Period:	Screening		Intervention													Notes:	
Scheduled Day	Screening/Rescreening ^b	EDS SOC Washout Before Randomization (Remote Visit Through Phone Call)	D1												D2	Screening procedures to be completed within approximately 28 days ± 7 days from randomization	
CCI			CCI														
Safety Procedures																	
C-SSRS Baseline/Screening	X																Sec. 8.3.8.1
Full physical examination	X		X													X	Sec. 8.3.1 In each treatment period full PE will be conducted as follows: Dose 1: Predose, and 24-hour postdose 1 Dose 2: 24-hour postdose 2 Predose physical exam may be conducted upon admission within 24 hours of dosing.
General neurological examination	X		X														Sec. 8.3.2, Appendix 10 (Sec 10.10.1) Applicable at Screening and at each treatment period at Predose #1 only Predose #1 general NE, may be conducted upon admission within 24 hours of dosing

Part 1/All Panels/All Periods/Dose 1 and Dose 2 ^a																
Study Period:	Screening		Intervention													Notes:
Scheduled Day	Screening/Rescreening ^b	EDS SOC Washout Before Randomization (Remote Visit Through Phone Call)	D1											D2	Screening procedures to be completed within approximately 28 days ± 7 days from randomization	
CCI			CCI													
Targeted neurological examination							X					X			X	Sec. 8.3.2, Appendix 10 (Sec 10.10.2) In each treatment period, targeted NE will be conducted as follows: CCI
Height	X															Sec. 8.3.1
Weight	X															Sec. 8.3.1, 8.3.3 BMI to be taken only at Screening
Resting VS (HR, BP)	X		X		X	X	X	X	X	X	X				X	CCI

Part 1/All Panels/All Periods/Dose 1 and Dose 2 ^a															
Study Period:	Screening		Intervention												Notes:
Scheduled Day	Screening/Rescreening ^b	EDS SOC Washout Before Randomization (Remote Visit Through Phone Call)	D1											D2	Screening procedures to be completed within approximately 28 days ± 7 days from randomization
CCI			CCI												
Orthostatic VS (HR, BP)	X		X				X		X		X			X	Sec 8.3.4.2 In each treatment period orthostatic VS will be measured as follow: CCI
RR and BT	X		X				X				X			X	Sec. 8.3.4.1 In each treatment period RR and BT will be measured as follow: CCI
12-lead ECG	X		X			X	X	X		X	X			X	Sec. 8.3.5, Appendix 8 In each treatment period all ECGs are to be conducted in triplicate. At screening and poststudy, ECG will be conducted as single measurements. CCI

Part 1/All Panels/All Periods/Dose 1 and Dose 2 ^a																
Study Period:	Screening		Intervention													Notes:
Scheduled Day	Screening/Rescreening ^b	EDS SOC Washout Before Randomization (Remote Visit Through Phone Call)	D1											D2	Screening procedures to be completed within approximately 28 days ± 7 days from randomization	
CCI			CCI													
															CCI	
Serum (hCG; POCBP only)	X															Sec. 8.3.6, Appendix 2
Urine Pregnancy Test (POCBP only)			X													Sec. 5.1, 8.3.7 Urine pregnancy test to be completed in each treatment period
Serum FSH - (POCBP only)	X															Appendices 2 and 5
HIV, hepatitis B and C screen (per site SOP)	X															Sec. 5.2, Appendix 2
Drug screen (per site SOP)	X		X													Appendix 2 Screening drug screen is mandatory, any additional drug screens are conducted per site SOP. Alcohol test will be conducted using a breathalyzer. To be collected in Period 1 only Predose drug screen and alcohol test may be collected upon admission within 24 hours of dosing.

Part 1/All Panels/All Periods/Dose 1 and Dose 2 ^a																
Study Period:	Screening		Intervention													Notes:
Scheduled Day	Screening/Rescreening ^b	EDS SOC Washout Before Randomization (Remote Visit Through Phone Call)	D1												D2	Screening procedures to be completed within approximately 28 days ± 7 days from randomization
CCI			CCI													
Hematology, Chemistry, Urinalysis	X		X													Sec. 8.3.6, Appendix 2 In Period 1 only, blood for safety laboratory tests will be collected as follow: Dose 1: Predose
Safety Phone Calls		X														Sec. 8.3.10.1, 8.1.5.1 Washout period may vary based on the EDS SOC
AE/SAE review	X	X	X	X	X	X	X	X	X	X	X	X	X	X	X	Sec. 8.4, Appendix 3
Pharmacokinetics																
Blood for Plasma MK-6552 and or Metabolites Assay			X		X	X	X	X	X	X	X	X	X	X	X	Sec. 8.6.1, 8.11.5 In each treatment period, PK blood collection will be as follow: CCI

Part 1/All Panels/All Periods/Dose 1 and Dose 2 ^a																
Study Period:	Screening		Intervention													Notes:
Scheduled Day	Screening/Rescreening ^b	EDS SOC Washout Before Randomization (Remote Visit Through Phone Call)	D1											D2	Screening procedures to be completed within approximately 28 days ± 7 days from randomization	
CCI			CCI													
Pharmacodynamics																
PSG	X															Sec. 8.7.1
CCI	X		X				X					X	X			Sec. 8.7.3 In each treatment period completed at: CCI
CCI			X											X		Sec. 8.7.4 CCI

Part 1/All Panels/All Periods/Dose 1 and Dose 2 ^a																
Study Period:	Screening			Intervention												Notes:
Scheduled Day	Screening/Rescreening ^b	EDS SOC Washout Before Randomization (Remote Visit Through Phone Call)	D1												D2	Screening procedures to be completed within approximately 28 days ± 7 days from randomization
CCI			CCI													
Biomarkers																
Blood for Planned Genetic Analysis			X													Sec. 8.8.1 Collected from enrolled participant in Period 1 only.
Blood for HLA DQB1*0602 Genotyping	X															Sec. 8.8
AE=adverse event; BDS=blood drug screen; BMI=body mass index; BP=blood pressure; BT=body temperature; CRU=clinical research unit; C-SSRS=Columbia-Suicide Severity Rating Scale; D=day; EC=exclusion criteria; ECG=electrocardiogram; EDS=excessive daytime sleepiness; FBR=future biomedical research; FSH=follicle-stimulating hormone; hCG=human chorionic gonadotropin; HIV=human immunodeficiency virus; HLA-DQB1=human leukocyte antigen DQ Beta 1; HR=heart rate; IC=inclusion criteria; ID=identification; CCI; NE=neurological examination; PE=physical examination; PGA=planned genetic analysis; PK=pharmacokinetic; POCBP=participant of childbearing potential; CCI; RR=respiratory rate; SAE=serious adverse event; SOC=standard of care; SOP=standard operating procedure; UDS=urine drug screen; VS=vital signs.																
^{a.} Predose time-point is applicable to Dose #1 only. ^{b.} Rescreening is defined as a separate screening period. All activities conducted during Screening must be completed as part of Rescreening. See Section 8.11.1.																

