Safety/Study Medication Compliance Phone Calls											X	X		Sec 8.3.10.2 CCI
C-SSRS Since Last Assessment	X						X							Sec 8.3.8.1 CCI

Part 2/Panel A/All Periods/Dose 1 and Dose 2 ^a													
												Poststudy	Notes:
CCI													
Blood for Plasma MK-6552 and or Metabolites Assay	X				X		X	X			X	X	Sec 8.6.1 In each treatment period, PK blood collection will CCI
Pharmacodynamic													
CCI													
MWT				X		X	X	X					Sec 8.7.2, 8.11.5 CCI

Part 2/Panel A/All Periods/Dose 1 and Dose 2 ^a													
												Poststudy	Notes:
CCI													
CCI	X		X			X							Sec 8.7.3 CCI
CCI	X										X		Sec 8.7.4 CCI
AE=adverse event; BDS=blood drug screen; BP=blood pressure; C-SSRS=Columbia-Suicide Severity Rating Scale; ECG=electrocardiogram; FBR=future biomedical research; FSH=follicle-stimulating hormone; hCG=human chorionic gonadotropin; HR=heart rate; ID=identification; CCI PGA=planned genetic analysis; POCP=participant of childbearing potential; CCI; PE=physical examination; NE=neurological examination; SAE=serious adverse event; SOP=standard operating procedure; UDS=urine drug screen; VS=vital signs.													
^a Predose time-point is applicable to Dose #1 only.													

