3 HYPOTHESES, OBJECTIVES, AND ENDPOINTS

Hypotheses are aligned with objectives in the Objectives and Endpoints table.

Participants with NT1 18 to 55 years of age inclusive.

Primary Objective	Primary Endpoint
To evaluate the safety and tolerability of a single-day CCI and multiple-day CCI administration of M with Narcolepsy Type 1.	Adverse events, discontinuation of study intervention due to adverse events
To assess the pharmacodynamic profile of MK-6552 CCI after multiple-day administration in participants with Narcolepsy Type 1. CCI	CCI
Secondary Objectives	Secondary Endpoints
To characterize the plasma pharmacokinetics of MK-6552 following administration of single-day bid CCI oral doses in participants with Narcolepsy Type 1. CCI	CCI CCI CCI

Tertiary/Exploratory Objectives	Tertiary/Exploratory Endpoints
CCI [REDACTED]	[REDACTED]
[REDACTED]	[REDACTED]
[REDACTED]	[REDACTED]
[REDACTED]	[REDACTED]
To explore the relationship between genetic variation and response to the treatment(s) administered, and mechanisms of disease. Variation across the human genome may be analyzed for association with clinical data collected in the study	Germline genetic variation and association to clinical data collected in this study

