4.2.3 Rational for Suicidal Ideation and Behavior Monitoring

Prospective assessment of suicidal ideation and behavior will be performed in this study using the C-SSRS. This assessment is being conducted in compliance with the 2012 FDA guidance requiring prospective assessment in clinical studies conducted under IND applications and studies that are intended for submission in a NDA to the Neurology or Psychiatry Divisions of the FDA or BLA, as well as assessment in studies that fall within the guidance for other reasons (eg, CNS active/penetrant compounds, and known mechanisms or indications for which suicidal ideation/behavior has been previously identified as a potential concern).

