8.3.8 Suicidal Ideation and Behavior Monitoring

8.3.8.1 Clinical Assessments for Suicidal Ideation and Behavior Monitoring

Suicidal ideation and behavior will be prospectively assessed during this study using the C-SSRS. The C-SSRS should be administered by trained raters at the time points indicated in the SoA. In addition, C-SSRS will be administered at any unscheduled visit where safety assessments are performed. The C-SSRS will not be routinely administered at visits with a sole purpose of PK sampling and/or witnessed study intervention administration. Site staff should review the contents of the C-SSRS for completeness.

If the C-SSRS is administered by someone other than the investigator, consider providing the completed C-SSRS to the investigator for review, before their assessment of the participant and to further inform their evaluation.

The C-SSRS is not explicit about whether the participant specifically has ideation at the time of screening. If a participant reports a prior history of ideation/behavior at screening, the assessor should also inquire and document if this is also present at the time of the Screening Visit.

Participants who at any time during this study report suicidal ideation or behavior that is considered to be an AE, either between visits or during visit interviews, must be assessed by the investigator. Participants who report suicidal ideation with intent, with or without a plan or method (ie, a positive response to items 4 or 5 in the assessment of suicidal ideation on the C-SSRS) or suicidal behavior must be evaluated that day by a psychiatrist or other trained mental health professional who is a licensed psychologist, social worker, or mental health nurse practitioner (or comparable professional qualification in countries outside the United States). After that evaluation, only those participants whose suicidal ideation is considered by the evaluator to be passive, and who expressly deny any intent to act, and who, after evaluation, are not judged to be at serious risk for self-harm during the course of the study may continue in the study; other participants must be discontinued from study participation and receive appropriate clinical follow-up care to ensure their safety. In addition, all AEs of suicidal ideation or behavior must be recorded as an ECI (see Section 8.4.7). Sites are to

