8.11.4 Poststudy

Participants will be required to return to clinic approximately 14 days after the last dose of study intervention for the poststudy visit. If the poststudy visit occurs less than 14 days after the last dose of study intervention, a subsequent follow-up telephone call should be made at 14 days post the last dose of study intervention to determine if any AEs have occurred since the poststudy clinic visit.

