9.3 Analysis Endpoints

9.3.1 Primary Endpoints

Safety: Primary safety endpoints will include all types of adverse experiences, in addition to laboratory safety tests, ECGs, C-SSRS and vital signs.

CCI [REDACTED]

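### C-SSRS is not scheduled after any Part 1 dose or at the poststudy visit, so participants who leave during Part 1 have no scheduled post-dose assessment and the poststudy follow-up has none

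*Combined protocol and SAP*

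**What the plan says.** **Status of the scale.** Section 9.3.1 states: "Primary safety endpoints will include all types of adverse experiences, in addition to laboratory safety tests, ECGs, C-SSRS and vital signs". The objectives table in Section 3 gives a narrower primary safety endpoint: "Adverse events, discontinuation of study intervention due to adverse events". Section 4.2.3 commits the study to it in these words: "Prospective assessment of suicidal ideation and behavior will be performed in this study using the C-SSRS". Under Section 9.5.1 the responses are listed and not otherwise summarised.

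**When it is given.** Section 8.3.8.1 ties routine use to the schedule: "The C-SSRS should be administered by trained raters at the time points indicated in the SoA". It adds that "C-SSRS will be administered at any unscheduled visit where safety assessments are performed", and it exempts visits made solely for PK sampling or witnessed dosing.

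**The schedules.** Section 1.3.1 (Part 1) has a single row, "C-SSRS Baseline/Screening", with one mark, at Screening. Sections 1.3.2 and 1.3.3 (Part 2, Panels A and B) each have a row "C-SSRS Since Last Assessment" with two marks and an empty Poststudy cell.

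**After the last dose.** Section 8.11.4 says: "Participants will be required to return to clinic approximately 14 days after the last dose of study intervention for the poststudy visit". Section 8.1.9 says that anyone who discontinues may be asked to come for that visit, or may have the poststudy procedures done at or soon after discontinuation.

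**The concern.** The study is the first exposure of participants with narcolepsy type 1 to a centrally acting compound, and Part 1 is where the dose is raised. A scale adopted for prospective monitoring would be expected at least once after dosing in every treated participant, and once in follow-up. As scheduled, neither is assured.

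A participant who leaves during Part 1 belongs to the safety population in Section 9.4.1, since one dose is enough to qualify. That participant's C-SSRS listing could nevertheless contain only the screening value. The poststudy visit, which closes the 14-day reporting window and follows the return to usual treatment, has no structured assessment for anyone.

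What is at stake is completeness of safety ascertainment. No hypothesis test or estimate depends on the scale.

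**Working it through.** This is a check of the schedules against the text. The plan gives no figure to reproduce.

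1. **Part 1 marks.** The schema has 4 periods and Section 1.3.1 gives 2 doses per period, so up to 4 × 2 = 8 doses. C-SSRS marks: 1 at Screening, 0 on Day 1 or Day 2 of any period. The row's note holds only a section reference, with no redaction that could hide further times.

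2. **Part 2 marks.** In the extracted tables for both panels, the C-SSRS row is marked in columns 1 and 7. Poststudy is column 13 and is blank. Neighbouring rows show that this column is used: the urine pregnancy test, the hematology, chemistry and urinalysis row, and AE/SAE review are all marked there. Sections 8.3.4.1 and 8.3.5 confirm in text that poststudy blood pressure, heart rate and ECG are taken.

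3. **The plan's own trigger.** Section 8.3.8.1 requires the scale at any unscheduled visit with safety assessments. The poststudy visit has safety assessments and is not solely for PK or witnessed dosing. An unscheduled safety visit therefore calls for the C-SSRS, while the scheduled final safety visit does not.

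4. **Leaving during Part 1.** Section 8.1.9 leads to the poststudy procedures, which omit the scale (step 2). Section 7.1 keeps discontinuers in the study as set out in Sections 1.3 and 8.1.9, and Section 8.11.3 allows a discretionary subset of scheduled procedures. None of these guarantees a C-SSRS. Scheduled post-dose assessments for this participant: 0.

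5. **Reaching Part 2.** The first Part 2 mark, apparently predose, looks back over Part 1, so there is at least one assessment after Part 1 dosing. Scheduled assessments at the follow-up visit: 0.

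6. **How many could be affected.** No Part 1 dropout rate is given. Purely as an assumption, let each of 24 participants leave during Part 1 independently with probability d. The expected number of leavers is 24d, and the chance of at least one is 1 − (1 − d)^24.

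| Assumed d | Expected leavers | Chance of at least one |
|---|---|---|
| 5% | 1.2 | 71% |
| 10% | 2.4 | 92% |
| 20% | 4.8 | 99.5% |

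The table shows only that one such participant is plausible at modest rates. It says nothing about how often suicidal ideation or behavior would occur.

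**The case against.** The strongest reply is that surveillance does not stop where the questionnaire does. AE/SAE review is marked throughout Part 1 and at Poststudy. Suicidal ideation and behavior are events of clinical interest (Section 8.4.7), and reporting runs to 14 days after cessation, with a telephone call if the poststudy visit is early. Part 1 participants stay in the unit until at least 24 hours after the second dose. An unscheduled discontinuation visit with safety assessments would trigger the scale. All of this stands and keeps the point modest. It does not close the gap: Section 8.4.2 prefers open-ended questioning for adverse events, which is not the structured assessment that Section 4.2.3 promises.

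Three stronger readings are tempting, and the documents do not support them.

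- A reader might infer that 24 − 16 = 8 of 24 participants (33%) could finish without a post-dose C-SSRS. The 16 is a count of evaluable participants, not of Part 1 completers. A participant who is not evaluable may have completed Part 2 with every C-SSRS, and replacements are allowed (Section 5.5).
- A reader might count 24 × 4 = 96 Part 1 dosing days as unassessed. For anyone reaching Part 2, the look-back covers them.
- A reader might conclude that missing values will track poor tolerability. Section 6.6 lets a participant for whom escalation is not justified repeat a dose, receive a lower one or go on to Part 2, so poor tolerability need not mean leaving.

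It is also fair to say that the C-SSRS is primary only under Section 9.3.1 and is merely listed. That lowers the stakes, but the conflict with Sections 4.2.3 and 8.3.8.1 remains whichever status is right.

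**Conclusion.** The point holds in a limited form. Participants who leave during Part 1 have no scheduled post-dose C-SSRS. For all others, none is scheduled at the poststudy visit, the planned follow-up contact about 14 days after the last dose. Those who stop during Part 2 do have a scheduled assessment after Part 1 dosing, though not necessarily one after their last dose. Sections 3 and 9.3.1 also disagree on whether the scale is a primary endpoint.

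The number of participants affected cannot be stated. The consequence is incomplete safety ascertainment, not bias in an estimate.

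The conclusion rests on reading the blank cells as intended. The tables were extracted from PDF, and the Part 2 column headings and C-SSRS notes are redacted. The exact Part 2 times, including whether the second mark falls before or after that day's last dose, therefore cannot be confirmed. A redacted note could in principle add a time, but the Poststudy cell would then need correcting to match.

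**What to change.** - In Sections 1.3.2 and 1.3.3, mark "C-SSRS Since Last Assessment" in the Poststudy column.
- In Section 8.1.9, state that the C-SSRS is among the procedures done for participants who discontinue in either part. Keep the discretionary subset in Section 8.11.3 consistent with this.
- Make Sections 3 and 9.3.1 agree on whether the C-SSRS is a primary safety endpoint.

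The cost is one extra short questionnaire per participant at a visit that already exists, given by raters already trained for the study, plus the wording changes. Adding the scale at discharge from each Part 1 period would tie responses more closely to dose level, but nothing in the documents requires it and it is optional.
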